Blood samples for clinical safety labs and vitamin D testing and will be obtained. In addition, blood samples will be collected for assay of serum estradiol prior to dosing on Day 1 and at designated study visits, and to measure plasma concentrations of elagolix and norethindrone at designated study visits. For subjects who consent, 3 separate DNA (Deoxyribonucleic acid) and RNA (Ribonucleic acid) pharmacogenetic (PG) blood samples and 2 endometrial samples will be collected. Pregnancy tests will be performed at each monthly visit throughout the Treatment Period. Urine pregnancy test kits will be provided to subjects for use at home for the study visits when subjects are not required to come into the clinic/site. Subjects will self-administer the tests and report the results to the site at the phone contact visits. Subjects will be counseled at each visit on consistent, appropriate and effective forms of dual non-hormonal contraception to promote pregnancy prevention. A positive urine pregnancy test must be confirmed with a serum pregnancy test. A positive serum pregnancy test at any time will necessitate discontinuation from the Treatment Period.

Additional detail regarding study procedures during the Treatment Period is provided in Section 5.3.1.1 and Appendix C, Study Activities.

Follow-Up Period

Subjects will enter the Follow-Up Period for 12 months to assess bone recovery after up to 48 months of treatment. Subjects who prematurely discontinue from the study at the time of or after the Treatment Period Month 6 visit will enter the Follow-Up Period.

DXA scans will be obtained at designated visits as described in Appendix C. Additional study procedures will be performed at designated study visits as outlined in Appendix C. Adverse event collection is detailed in Section 6.1.4 and Appendix C. Concomitant medication use will be reviewed at on-site visits.

Additional detail regarding study procedures during the Follow-Up Period is provided in Section 5.3.1.1 and Appendix C, Study Activities.

COVID-19 Pandemic-Related Acceptable Protocol Modifications

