5.2.3.3 Prohibited Therapy

All hormonal forms of birth control (except the emergency contraceptive pill, levonorgestrel 1.5 mg [such as Plan B®], or ulipristal acetate 30 mg [such as Ella® or EllaOne®]) are prohibited during Washout, Screening, Treatment and until the Follow-Up Month 1 visit. Subjects may start hormonal contraception after completion of Follow-Up Month 1, provided that the subject has a documented menstrual period (menses) after the Treatment Period and prior to that visit. For subjects who are prescribed/administered the emergency contraceptive pill during the study, the information should be captured in the source documents and eCRF.

To protect subject safety and to minimize confounding the study results, the following concomitant medications are prohibited during the study as specified below:

[figure not shown]

Table 2. Prohibited Medications

Prohibited During the Washout, Screening, Treatment, and Follow-Up Periods			
GnRH agonist	Leuprolide acetate (Lupron®)		
Prohibited During the Washout, Screening and Treatment Periods and thru Follow-Up Month 1			
Hormonal Medications and Non-hormonal Estrogen Supplements, such as:	GnRH agonist: nafarelin acetate (Synarel®), goserelin acetate (Zoladex®) Danazol (Danocrine®, Cyclomen®) Medroxyprogesterone Acetate (Depo-Provera®, Provera®) Oral contraceptives Other progestins (oral, vaginal, IUDs, implantable) Levonorgestrel (except emergency contraception, i.e., levonorgestrel 1.5 mg) Spironolactone Mifepristone Ulipristal acetate (except emergency contraception, i.e., ulipristal acetate 30 mg) Testosterone preparations Tamoxifen Bromocriptine (Parlodel®) Cabergoline (Dostinex®) Raloxifene (Evista®, Optruma, or generics) Bazedoxifene (Conbriza) Aromatase Inhibitors (e.g., Anastrozole [Arimidex®], Exemestane [Aromasin®]) Natural Estrogen preparations or herbal remedies/supplements to treat premenstrual or gynecological problems (e.g., soy-containing supplements, black cohosh)		

[figure not shown]

Table 2. Prohibited Medications (Continued)

Prohibited During the Screening and Treatment Periods			
Immediate Release (IR) Opioid Analgesics, such as:	Oxymorphone Hydromorphone Morphine Buprenorphine Except for short-term use as noted below.		
Long-acting, Controlled Release (CR), Extended Release (ER) or Transdermal Opioid Analgesics, such as:	CR/ER Morphine CR/ER Hydromorphone CR/ER Oxymorphone CR/ER Oxycodone ER Tapentadol ER Tramadol Fentanyl Methadone Levorphanol Buprenorphine		

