Intravenous Analgesics, such as:	Fentanyl Morphine Buprenorphine		
Synthetic Prostaglandin E1 Analogs, such as:	Misoprostol (Cytotec [®] , Arthrotec [®]) These medications may influence bleeding and should not be taken during the time noted above. However, use for the endometrial biopsy procedure is permitted, if needed.		
Prohibited 1 Month Prior to Day 1 and D	uring the Treatment Period		
Moderate or strong CYP3A ⁸ Inducers, such as:	Moderate Inducers: Bosentan Efavirenz Etravirine Modafinil Strong Inducers: St. John's Wort Rifampin Carbamazepine Phenytoin Mitotane Dexamethasone (chronic use)		

[figure not shown]

Table 2. Prohibited Medications (Continued)

Prohibited During the Screening, Treatment, and Follow-Up Periods			
Osteoporosis Medications (Bisphosphonates, RANKL Inhibitors, Anabolic Bone Agents or rPTH), such as:	denosumab, teriparatide Fosamax [®] , Boniva [®] , Reclast [®] , XGEVA [®] , Forteo [®]		
Glucocorticoids/Corticosteroids, systemic administration (oral, IM or IV)	Except for short-term use as noted below.		
Cannabinoids (including marijuana use)			
Other Teratogens, such as:	Topiramate, Accutane® and other oral retinoids		
GnRH antagonists (including investigational ones), such as:	Orilissa [®] , relugolix		

Any analgesic medications used to specifically treat endometriosis-associated pain, with the exception of the protocol-specified allowable rescue medications outlined in Section 5.2.3.4, are not permitted during the study (Screening and Treatment Periods). Prophylactic use (i.e., on a standing basis or for prevention of pain) of any analgesics for endometriosis-associated pain (including protocol specified rescue analgesics) is likewise prohibited.

Short-term use (no longer than 2 weeks per occurrence) of immediate-release opioids/opioid-containing products or systemic glucocorticoids/corticosteroids to manage acute conditions not related to endometriosis-associated pain, is allowed during the Treatment Period. A maximum of 6 weeks (total of 42 days) over the 48 month Treatment Period is allowed during a subject's participation. If the subject requires more than 2 weeks duration per occurrence or more than 6 weeks (total of 42 days) over the 48 month Treatment Period, their continued participation in the study must be reviewed with the AbbVie TA MD.

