DXA scans of the lumbar spine, total hip, and femoral neck will be obtained at Follow-Up Months 6 and 12.

COVID-19 Pandemic-Related Acceptable Protocol Modifications

Due to the COVID-19 pandemic, if the subject is unable to complete the DXA at its scheduled time, it can be delayed up to one month. Should the delay be longer, AbbVie should be notified for further guidance.

Endometrial Biopsy

Endometrial biopsies will be performed during the Screening and Treatment Periods, as indicated in Appendix C. Instructions on endometrial biopsy collection, processing and shipping procedures will be provided by the central laboratory selected for this study. All central laboratory pathologists will be blinded to the subjects' treatment group assignments. Endometrial biopsies will be independently read by two qualified central laboratory pathologists. If the results are discrepant, the biopsy will be read by a third central laboratory pathologist to facilitate resolution and the worst case reading (of all three reads) will be taken as the final diagnosis. A final pathology report containing the final diagnosis from the central laboratory will be issued to the Investigator in all cases.

Prior to performing the endometrial biopsy, a negative urine pregnancy result must be obtained on the day of the procedure. Pre-medication for the endometrial biopsy procedure is allowable, e.g., at the investigator's discretion, misoprostol for cervical dilation is allowable. In addition, lidocaine may be used as local anesthesia on the cervix. Any medications used for the procedure should be recorded in source documents and on the appropriate eCRF. The Investigator should write a brief procedure note in the source

documentation noting the depth of placement of the Pipelle during the procedure. If an endometrial biopsy cannot be performed because of anatomical reasons, the AbbVie TA MD should be consulted for further guidance.

If the endometrial biopsy is performed on the same day as the Pap test or transvaginal ultrasound, the endometrial biopsy should be performed after the Pap test and transvaginal ultrasound.

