5.4 Removal of Subjects from Therapy or Assessment

Each subject has the right to withdraw from the study at any time. In addition, the Investigator may discontinue a subject from the study at any time if the Investigator considers it necessary for any reason, including the occurrence of an adverse event or noncompliance with the protocol. Subjects who withdraw from the study will not be replaced unless it is mutually agreed upon, in writing, by the Investigator and AbbVie. Subjects will be withdrawn from study drug treatment and/or the study if any of the following occur:

- The subject decides to withdraw consent for any reason
- The investigator believes it is in the best interest of the subject
- Clinically significant deterioration of the subject's medical status as determined by the Investigator
- The subject becomes pregnant or subject has a positive serum pregnancy test
- The subject has ALT or AST elevation > 5 times the upper limit of normal, confirmed upon repeat testing
- The subject develops clinically significant gynecological findings or condition on either the TVU (confirmed by repeat TVU and/or SIS and/or office hysteroscopy) or endometrial biopsy that in the opinion of the Investigator or AbbVie TA MD would preclude the subject from continuing in the Treatment Period due to safety reasons
- The results of any post-baseline DXA prior to Month 48 document a Z-score (for subjects ≤ 40 years of age) or T-score (for subjects ≥ 40 years of age) of

- < -2.5, a BMD decrease from baseline of > 8% in the lumbar spine, total hip or femoral neck, or due to TA MD assessment when the BMD percent change from baseline cannot be provided by the central reader
- The subject will require ongoing use of prohibited medications to manage or treat her endometriosis or endometriosis-associated pain in the opinion of the Investigator or AbbVie TA MD
- The subject requires use of prohibited medications to manage or treat bone mineral density changes during the Treatment Period as described in Section 5.2.3.3. Subject continuation in the Follow-Up Period is at the discretion of the AbbVie TA MD.
- The subject requires surgical intervention for treatment of endometriosis or uterine bleeding (e.g., laparoscopy, hysterectomy, ovarian cystectomy)
- The Investigator and AbbVie TA MD deems it appropriate to protect the subject because the subject expresses suicidal ideation on the C-SSRS or via clinical interview at any time during the study.

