9.5.2.2 Bone Mineral Density during the Follow-up Period

BMD

A summary of continuous BMD at each scheduled assessment will be provided by treatment group during the Follow-up Period. This summary will include the sample size, mean, SD, median, minimum, and maximum. This analysis will be repeated including subjects who switch machine manufacturer type (Lunar or Hologic).

The analysis of percent change in BMD from baseline to each relevant visit during the Follow-up Period will be based on an ANCOVA model with treatment as the main effect

and baseline value of corresponding parameter as a covariate. No comparison will be performed during the Follow-up Period. This analysis will be repeated including subjects who switch machine manufacturer type (Lunar or Hologic).

The analysis of percent change in BMD from baseline will be repeated for the following subset of subjects:

- subjects who have a Treatment Month X (e.g., Month 12) scan and a Follow-up Month Y (e.g., Follow-up Month 6) scan and premature discontinue prior to next scheduled assessments.

The number and percentage of subjects with percent change from Baseline to each scheduled assessment during the Follow-up Period in mutually exclusive categories of BMD decrease: $\leq 0\%$, $> 0\% - \leq 1.5\%$, $> 1.5\% - \leq 3\%$, $> 3\% - \leq 4\%$, $> 4\% - \leq 5\%$, $> 5\% - < 8\%$, and $\geq 8\%$ will be summarized by treatment group.

In addition, the number and percentage of subjects with percent change from final on-treatment to each scheduled assessment during the Follow-up Period in mutually exclusive categories of BMD decrease: $\leq 0\%$, $> 0\% - \leq 1.5\%$, $> 1.5\% - \leq 3\%$, $> 3\% - \leq 4\%$, $> 4\% - \leq 5\%$, $> 5\% - < 8\%$, and $\geq 8\%$ will be summarized by treatment group.

For the purpose of assessing post-treatment BMD recovery, the following summaries will be provided. The "recovery" statistic was defined as

Recovery at Follow-up Month X = $100 \times ((\% \text{ change from baseline to final}) - (\% \text{ change from baseline to Follow-up Month X})) / (\% \text{ change from baseline to final})$

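### The follow-up bone-recovery summaries take no account of hormonal or bone drugs started after study drug stops, so they can mix off-drug recovery with the effect of another drug

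*SAP*

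**What the plan says.** **Purpose and timing.** Protocol 5.1 gives the reason for Follow-Up: "Subjects will enter the Follow-Up Period for 12 months to assess bone recovery after up to 48 months of treatment". Protocol 5.3.1.1 sets the scans: "DXA scans of the lumbar spine, total hip, and femoral neck will be obtained at Follow-Up Months 6 and 12".

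**Drugs allowed in that window.** In Table 2 (Protocol 5.2.3.3) a long list of hormonal agents carries the heading "Prohibited During the Washout, Screening and Treatment Periods and thru Follow-Up Month 1". It includes nafarelin, goserelin, danazol, medroxyprogesterone, oral contraceptives, raloxifene, bazedoxifene and aromatase inhibitors. Protocol 5.2.3.3 and 5.2.4 let hormonal contraception begin after the Follow-Up Month 1 visit once menses have been documented. Section 5.2.4 also covers restarting it when menses have not returned.

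**Drugs still barred.** Leuprolide is barred through Follow-Up. Osteoporosis drugs, systemic corticosteroids and GnRH antagonists fall under "Prohibited During the Screening, Treatment, and Follow-Up Periods". Protocol 5.4 then says, of a woman who needs prohibited medication for BMD changes during treatment: "Subject continuation in the Follow-Up Period is at the discretion of the AbbVie TA MD".

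**Analysis.** SAP 9.5.2.2 opens the recovery outputs with "For the purpose of assessing post-treatment BMD recovery, the following summaries will be provided". The recovery subsets are defined by a decrease at the final on-treatment scan and by time of discontinuation. The only general exclusion, in SAP 9.5.2, is a change of scanner manufacturer. SAP 7.3 tabulates post-treatment medications but does not connect them to BMD.

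**The concern.** Readers will take the recovery figures as a description of what bone does once elagolix plus E2/NETA is withdrawn. The protocol itself ties bone to estradiol: section 5.6.4 attributes elagolix's BMD loss to estradiol suppression and notes that E2/NETA mitigates it, and section 5.6.2 repeats the link. The list released at Follow-Up Month 1 contains agents that supply estrogen and agents that suppress it. A woman who starts one before her Month 6 or Month 12 scan contributes a value that reflects two drugs, and nothing in SAP 9.5.2.2 shows this.

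The continued-loss listing is exposed in a particular way. It leaves out a woman whose BMD rises after Follow-Up Month 6. If that rise followed the start of another drug, she drops out of a safety listing for a reason unrelated to spontaneous recovery. A woman whose loss continued under renewed estrogen suppression would be listed with no sign of that.

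**Working it through.** **1. Exposure window.** The hormonal bar ends at Follow-Up Month 1 and the scans are at Months 6 and 12. Possible exposure before a scan is therefore up to 6 - 1 = 5 months and 12 - 1 = 11 months. Both scans lie inside the window.

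**2. The SAP's own example.** Recovery = 100 × (change to final - change to follow-up) / (change to final). With -2% at the end of treatment and -1% at Follow-Up Month 6: 100 × ((-2) - (-1)) / (-2) = 50%. This matches the SAP.

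**3. Sensitivity for one woman.** Suppose another drug moves her follow-up change by d percentage points (assumed). Recovery becomes 100 × ((-2) - (-1 + d)) / (-2) = 50 + 50d.

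| d (points) | Recovery |
|---|---|
| -1 | 0% |
| -0.5 | 25% |
| +0.5 | 75% |
| +1 | 100% |

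With a 2% loss, each half point of BMD moves her recovery by 25 points.

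**4. Sensitivity of the mean.** Suppose a share f of women use such a drug (assumed) and all others recover 50%. The mean is (1 - f) × 50 + f × (50 + 50d) = 50 + 50fd.

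| f | d = -1 | d = -0.5 | d = +0.5 | d = +1 |
|---|---|---|---|---|
| 10% | 45% | 47.5% | 52.5% | 55% |
| 20% | 40% | 45% | 55% | 60% |
| 40% | 30% | 40% | 60% | 70% |

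The mean moves by 2.5 to 20 points. The documents give neither f nor d, so this shows how sensitive the statistic is and does not estimate bias. If some drugs raise BMD and others lower it, the effects partly cancel in the mean while still spreading the distribution and its plot.

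**5. Is it handled elsewhere?** Across SAP 9.5.2.2, the percent-change model, the loss categories, the recovery summaries, the cumulative plots and the continued-loss listing contain no rule based on medication. SAP 7.3 shows how many women used a drug, but not whether use began before a scan or what their BMD did.

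**6. Can it be handled?** Yes. Protocol 5.2.3.2 requires the reason, dates and dose of all concomitant medication through Follow-Up, and Appendix C lists medication review at Follow-Up Months 1, 6 and 12.

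**The case against.** Several stronger readings are tempting, and the documents do not support them.

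- **That osteoporosis drugs are permitted in Follow-Up.** They are barred by Table 2. Protocol 5.4 adds a case-by-case decision, in line with the general rule in 5.2.3.3 that continued use of a prohibited drug is reviewed individually. That route has no link to Follow-Up Month 1. A bar with a reviewed exception is not clearly a contradiction, but the two places do not refer to each other.
- **That every follow-up scan is pooled.** Recovery is defined only for women with a decrease at the final on-treatment scan, scanner switchers are dropped by default, and the continued-loss listing applies loss thresholds. The pooling is across medication use only.
- **That use will be common, or concentrated in women with the largest loss.** No passage says so.
- **That scans before any other drug should be the main analysis.** If women with the largest loss were the ones treated, removing their scans would leave a selected group. The all-scan summary is a legitimate description of what happens after stopping.

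On importance, Protocol 8.1.7.4 rules out statistical testing in Follow-Up, and bone recovery is not among the objectives in Protocol 4.0. This limits the weight of the point. It does not close the gap, because recovery is the stated purpose of Follow-Up and no planned output separates off-drug recovery from recovery on another drug.

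**Conclusion.** The point stands in limited form. Both recovery scans fall where a broad list of hormonal agents is no longer barred, and SAP 9.5.2.2 summarises recovery, percent change and continued loss regardless of such use. The summaries can therefore mix off-drug recovery with another drug's effect, upward or downward.

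A reader might infer that the recovery results are biased by a known amount or in a known direction. The documents do not support that. The 30% to 70% range rests entirely on assumed shares and shifts applied to the SAP's example. Treating the released drugs as bone-active rests on the protocol's estradiol-bone link, which does not establish an effect for each agent listed.

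The matter concerns a descriptive safety analysis. The co-primary endpoints, the type I error plan and the key lumbar-spine comparisons at Months 6 and 12 are unaffected. It is an inexpensive improvement worth making.

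**What to change.** **In SAP 9.5.2.2:**

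- Keep the all-scan summaries as planned.
- Pre-specify a supplementary version of the percent-change and recovery summaries, at least for all women with a decrease at the final on-treatment scan. Exclude follow-up scans taken after the first post-treatment dose of a pre-listed drug: the Table 2 hormonal agents, osteoporosis drugs and systemic corticosteroids.
- Report the number of such users by treatment group.
- In the continued-loss listing, flag users with their start dates. Also show women who were left out of the listing because BMD rose after such a start.

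**In the protocol, separately:**

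- Reconcile the Table 2 rows. One bars leuprolide, labelled a GnRH agonist, for all of Follow-Up, while another bars the GnRH agonists nafarelin and goserelin only through Follow-Up Month 1.
- Cross-reference the discretion in section 5.4 to the Table 2 bar on osteoporosis drugs.

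The sponsor decides which rule applies in each case.

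**Cost.** SAP wording and extra tables across three anatomic sites and two visits, using data already collected. The supplementary analysis will have fewer scans and wider intervals, and it may be selective, which is why the all-scan version stays.

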6.1.4 Adverse Event Collection Period

All adverse events reported from the time of study drug administration until 30 days following discontinuation of study drug administration have elapsed will be collected, whether solicited or spontaneously reported by the subject. All nonserious adverse events of bone fracture, clinically significant BMD loss, or newly diagnosed medically-related bone condition will be collected during the Follow-Up Period, until the subject discontinues from study participation. In addition, serious adverse events and protocol-related nonserious adverse events will be collected from the time the subject signed the study-specific informed consent.

Adverse event information will be collected as shown in Figure 2.

SAEs and Nonserious AEs SAEs and Elicited and/or Spontaneously Protocol-Related Reported Nonserious AEs SAEs and Bone-related AEs End of Study Consent Study Drug Study 30 days After (end of Signed Stopped Drug Start Study Drug Follow-Up) Stopped

Figure 2. Adverse Event Collection

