The "recovery" statistic is the proportion of BMD decrease at the final treatment scan recovered at Follow-up Month X. For example, a subject who has a change of -2% at the end of treatment and has a change of -1% at Follow-up Month 6 has a recovery value of 50% at Follow-up Month 6. This statistic will only be defined for subjects who experienced a decrease from baseline at final treatment.

A continuous summary of recovery at each relevant visit during the Follow-up Period will be provided including mean, standard deviation, median, and a within-group 95% confidence interval for the following subset of subjects:

- All subjects who experienced a decrease from baseline at final treatment;
- Subjects who premature discontinue after Month 6 and on or prior to Month 12;
- Subjects who premature discontinue after Month 12 and on or prior to Month 18;
- Subjects who premature discontinue after Month 18 and on or prior to Month 24;
- Subjects who premature discontinue after Month 24 and on or prior to Month 30;
- Subjects who premature discontinue after Month 30 and on or prior to Month 36;
- Subjects who premature discontinue after Month 36 and on or prior to Month 42;
- Subjects who premature discontinue after Month 42 or completed the Treatment Period.

Additionally, the number and percentage of subjects in each of the following categories will be provided for the subset of subjects listed above: < 0%, 0 – 25%, > 25 – 50%, > 50 – 75%, > 75 – 100%, > 100%.

Bone loss will be defined as > 3% at the spine, > 4% at the total hip, or > 5% at the femoral neck. The following listings will be provided:

- Listing of subjects with bone loss from baseline to final on-treatment visit and have continued bone loss from final on-treatment to Follow-up visits will be provided. Subjects subsequently with an increase from Follow-up Month 6 to a subsequent Follow-up assessment will be excluded from this listing.

In addition, the following plots will be provided:

- Cumulative distribution function of recovery at Follow-up Month 6 and Follow-up Month 12.
- Percent change from baseline to treatment and follow-up months of interest.

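### SAP 9.5.2.2 summarises BMD recovery by the mean and CI of an unstable per-woman ratio, plans no paired mean rebound, and drops women from the continued-loss listing on any later rise

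*SAP*

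**What the plan says.** **Recovery.** SAP 9.5.2.2 defines recovery at Follow-up Month X, per woman, as 100 × (F − U) / F. F is her percent change from baseline to the final on-treatment scan and U her percent change from baseline to Follow-up Month X. There is no minimum size for F: "This statistic will only be defined for subjects who experienced a decrease from baseline at final treatment". A continuous summary "will be provided including mean, standard deviation, median, and a within-group 95% confidence interval", for all such women and for seven groups by time of stopping. Six recovery categories (from below 0% to above 100%) and a CDF at Follow-up Months 6 and 12 go with it.

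**Change from the final scan.** Apart from the ratio, this appears once, as counts of women by "percent change from final on-treatment to each scheduled assessment during the Follow-up Period". The classes are classes of decrease, and the first is ≤ 0%. The follow-up ANCOVA uses change from baseline. So does its repeat in "subjects who have a Treatment Month X (e.g., Month 12) scan and a Follow-up Month Y (e.g., Follow-up Month 6) scan and premature discontinue" before the next assessment, and so does the plot, "Percent change from baseline to treatment and follow-up months of interest".

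**Listing.** Bone loss means more than 3% at the spine, 4% at the total hip or 5% at the femoral neck. Women with bone loss at the final on-treatment visit and continued loss in follow-up are listed, with one exception: "Subjects subsequently with an increase from Follow-up Month 6 to a subsequent Follow-up assessment will be excluded from this listing".

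**Protocol.** Section 5.1 states the purpose: "Subjects will enter the Follow-Up Period for 12 months to assess bone recovery after up to 48 months of treatment". Section 5.3.1.1 puts the follow-up DXA scans at Months 6 and 12 only. Section 8.1.7.4 asks that follow-up change from baseline be compared with end-of-treatment change from baseline, without testing.

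**The concern.** There are three linked weaknesses in the output that is meant to show bone recovery.

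1. A ratio whose denominator can be arbitrarily close to zero has a mean, SD and normal-theory CI that a handful of women can control. These are the women who lost almost nothing and so carry the least information about recovery.
2. The natural quantity, the average BMD regained since the last on-treatment scan, has no planned mean and no interval. In the one direct tabulation, a gain of 0.1% and a gain of 5% fall in the same class.
3. With only two follow-up scans, the exclusion rule means that Month 12 is above Month 6 by any amount. Scan error alone can produce that, and a woman can leave the listing while still below her final on-treatment value.

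At stake is whether the recovery result can be read, and whether the listing of continuing loss is complete.

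**Working it through.** **Step 1: the SAP's own example.** F = −2%, U = −1%: 100 × (−2 − (−1)) / (−2) = 50%. It reproduces exactly.

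**Step 2: the same 1-point gain from other starting points**, 100 × 1 / |F|:

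| F | −8% | −2% | −0.5% | −0.1% |
|---|---|---|---|---|
| Recovery | 12.5% | 50% | 200% | 1,000% |

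A 1-point fall gives the same sizes with a minus sign. No assumption is involved.

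**Step 3: five women**, F = −4, −3, −3, −2, −0.1. The first four recover 50% (gains of 2, 1.5, 1.5 and 1 points).
- If the fifth falls 1 point to −1.1, her ratio is −1,000%. Mean (4 × 50 − 1,000)/5 = −160%, SD 470, median 50%, paired mean change (6 − 1)/5 = +1.0 point.
- If she rises 1 point to +0.9, her ratio is +1,000%. Mean (4 × 50 + 1,000)/5 = +240%, SD 425, median 50%, paired mean change (6 + 1)/5 = +1.4 points.

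**Step 4: simulation.** The documents give none of these inputs; all are assumptions. There are 300 women with final and follow-up scans. True final change is N(μ, SD 2%). Scan error has SD e at baseline (shared), final and follow-up, and true recovery is 50% in every woman. Each case has 20,000 trials, and the ratio is taken where the observed F < 0.

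| | Mildest (μ −4, e 0.5) | Middle (μ −2, e 1) | Worst (μ −1, e 1.5) |
|---|---|---|---|
| Women with a ratio | 291 | 238 | 190 |
| Of these, loss under 0.25 points | 0.9% | 3.8% | 5.2% |
| Mean ratio, 95% of trials | 19 to 83% | −231 to 346% | −519 to 649% |
| Mean ratio, middle half | 47–53% | 27–73% | 3–97% |
| Mean outside 0–100% | 3% | 28% | 48% |
| Median width of planned CI | 13 | 105 | 217 |
| Planned median, 95% of trials | 48–52% | 43–57% | 38–62% |

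The extreme limits of the mean vary between runs. CI coverage is 97–98%, so at 50% recovery the interval is mostly wide rather than wrong. A larger sample is not a dependable cure. In one assumed setting (μ −0.5, SD 1.5, e 1) the median SD of the ratio rose from 378 with 50 women to 616 with 200, and the CI half-width fell only from 105 to 85 instead of halving.

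**Step 5: the paired mean in all 300 women.** The variance of U − F is (0.5 × 2)² + 2e², and the CI width is 2 × 1.96 × √(variance/300).
- e = 0.5: variance 1.5, width 0.28 BMD points; expected rebound 0.5 × 4 = 2.
- e = 1: variance 3, width 0.39; expected rebound 1.
- e = 1.5: variance 5.5, width 0.53; expected rebound 0.5.

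Coverage is 95%. Relative to the quantity estimated, the widths are 14%, 39% and 106%. For the mean ratio they are 13/50 = 26%, 105/50 = 210% and 217/50 = 434%. Percent change taken from the final scan itself, rather than the difference of two changes from baseline, gives widths of 0.30, 0.40 and 0.54.

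**Step 6: selection on an observed decrease.** With equal scan errors, over μ = −1, −2, −4 and e = 0.5, 1, 1.5, the median ratio centres on 0–17% when true recovery is zero and on 83–100% when it is complete. With unequal errors at 50% recovery and μ = −2, it centres on 55% (baseline/final error 0.5/1.5) or 45% (1.5/0.5).

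**Step 7: the listing.** Example: final −5%, Month 6 −8.2%, Month 12 −8.1%. She is dropped, although she is 3.1 points below her final scan.

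For a woman losing a true t points between Months 6 and 12, the chance of an observed rise is Φ(−t / (e√2)). At t = 1 this is 8%, 24% and 32% for e = 0.5, 1 and 1.5. Among listed women it is higher, because low Month 6 readings are over-represented. Spine limit, μ = −1 to −4:

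| Reading of continued loss; true loss to Month 6, then to Month 12 | e = 0.5 | e = 1 | e = 1.5 |
|---|---|---|---|
| Any decrease; 1 then 1 point: dropped | 9% | 31–33% | 44–47% |
| Same: dropped while still below final value | 9% | 26% | 29–31% |
| Further > 3% required; 3 then 3 points: dropped | 0% | 4% | 15–18% |
| Further > 3% required; 2 then 2 points: dropped | 2% | 22–26% | 38–43% |

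With the 4% and 5% limits the first row becomes 9%, 32–36% and 45–51%.

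**The case against.** The SAP already plans robust output beside the mean: the median, six categories and a CDF. An inflated mean would be obvious next to them. This stands, and it is why only the mean, SD and CI are at issue.

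The sizes depend on inputs the documents do not give. In the mildest case the mean is usable. This also stands: the simulation shows a range, not a prediction. Steps 1 and 2 do not depend on it.

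On the rebound, if the matched subset were tabulated at both visits, the difference of its two means would be the mean rebound for those women. But that subset holds only premature discontinuers, so completers are left out, and no interval is planned. Protocol 8.1.7.4 asks only for a descriptive comparison of changes from baseline, so there is a gap but no breach.

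On the listing, dropping women whose BMD later rose is a coherent definition of uninterrupted loss. They still count in the change-from-final categories. Protocol 6.1.4 is a further safeguard: "All nonserious adverse events of bone fracture, clinically significant BMD loss, or newly diagnosed medically-related bone condition will be collected during the Follow-Up Period". Both points limit the harm. They do not justify a rule that scan error can trigger with no size limit. It is also true that the SAP does not say whether continued loss reuses the 3/4/5% limits, and the drop rates depend on that. In the 2-then-2-point case under the stricter reading, the women's true further loss at Month 6 is below the 3% limit, so they enter the list through scan error.

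**Conclusion.** All three parts hold; the point is minor. The instability of the mean ratio follows from its definition. Its size under the assumed inputs runs from tolerable (3% of trial means outside 0–100%) to unusable (48%), while the median and the paired mean change remain stable. The rebound since the last on-treatment scan has no planned mean or interval in the full set of women with both scans. Under the looser reading of continued loss, with 1 point truly lost in each half of follow-up, the exclusion rule removes about 9% to 47% of listed women for scan errors of 0.5 to 1.5%. Under the stricter reading the range is 0% to 43%. Follow-up BMD is descriptive, so no hypothesis test, endpoint or sample size is touched.

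**What to change.** In SAP 9.5.2.2:

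- Replace the mean, SD and 95% CI of individual recovery ratios with the group mean percent change from the final on-treatment scan to Follow-up Months 6 and 12, with 95% CI. Include all women with both scans, not only those with an observed decrease: at zero true recovery, that selection alone produced an apparent gain of about 0.1 to 0.5 points in simulation. Apply the same machine-switch exclusion as the rest of 9.5.2.
- Keep the median, categories and CDF of recovery as descriptive output, with one line noting the selection effect.
- In the listing, delete the exclusion sentence and show the Month 6-to-12 change as a column. While editing, state whether continued loss means any further decrease or a further loss beyond the 3/4/5% limits.

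The cost is SAP wording, revised table shells and a longer listing. No new data are needed.
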